If you uploaded a separate research protocol document in the 'Research Protocol' page, cite the applicable section and page numbers from that document in the answer boxes below.

1 * Describe the purpose, specific aims, or objectives of this research. State the hypothesis to be tested:

This is a phase I/II feasibility/preliminary efficacy randomized controlled trial in 54 patients with cancer who recently completed adjuvant treatment for cancer (e.g., chemotherapy, radiotherapy, surgery) to compare 12 weeks of the POSTHOC app as part of the Survivorship Care Plan vs. the usual care Survivorship Care Plan on total symptom burden.

Aim 1: To assess how many participants view or log data in the app at least 3 times per week over the 12-week study. We hypothesize that at least 75% of participants ($\geq 27/36$) will view or log data in the app at least 3 times per week.

Aim 2: To obtain a preliminary estimate of the effect of the POSTHOC app vs. usual care on cumulative patient-reported symptom burden. We hypothesize that the POSTHOC app will reduce cumulative symptom burden reported by patients compared to usual care, as measured by the sum of severities of the core patient-reported symptoms from the MD Anderson Symptom Inventory, including fatigue, insomnia, pain, appetite loss, dyspnea (shortness of breath), cognitive problems, nausea, distress, and sensory neuropathy.

Aim 3: To obtain a preliminary estimate of the effect of the POSTHOC app vs. usual care on patient-reported and objectively measured health behaviors (physical activity, diet, sleep). We hypothesize that the POSTHOC app will improve health behaviors compared to usual care, as measured by patient-reported physical activity (Global Physical Activity Questionnaire) and sleep (Insomnia Severity Index), as well as objective measurements of physical activity (e.g., daily steps) and sleep (e.g., sleep quality) from the activity tracker and diet (i.e., telephone-administered dietary assessment).

Exploratory aims: To assess the acceptability and usability of the POSTHOC app by participants in the POSTHOC intervention group at week 6 and week 12 using questionnaires.

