Mechanistic (exploratory) aims: To obtain preliminary estimates of the effects of the POSTHOC app vs. usual care on patient-reported symptoms including neuropathy (CIPN20), pain (Brief Pain Inventory), cognitive impairment (FACT-Cog), fatigue (Brief Fatigue Inventory), and anxiety and depression (Hospital Anxiety and Depression Scale and Distress Thermometer), as well as clinician-reported patient health (e.g., ECOG performance status), and healthcare utilization (e.g., number of unplanned medical encounters). In addition to questionnaires, we will also assess how key symptoms are affected using ecological momentary assessment.

1 To assess cross-sectional associations between health behaviors (physical activity, diet, sleep) and cumulative symptom burden at baseline.

2 To explore associations between changes in health behaviors (physical activity, diet, sleep) and cumulative symptom burden from baseline to 6 weeks and baseline to 12 weeks.

3 To explore associations between adherence to the intervention and changes in the same measures.

2 * Discuss the research design including but not limited to such issues as: probability of group assignment, potential for subject to be randomized to placebo group, use of control subjects, etc.:

This is a phase I/II feasibility/preliminary efficacy randomized controlled trial. Participants will be randomized 2:1, intervention (n=36): usual care (n=18). There is a 67% chance of any given participant to be in the intervention group, and a 33% chance of any given participant to be in the usual care group.

Neither the study PI nor the coordinators will be blinded due to their active involvement in participant interaction and data collection. The participants cannot be blinded due to the nature of the intervention.

3 * Describe the relevant prior experience and gaps in current knowledge. Describe any relevant preliminary data:

After completion of cancer treatment, people are faced with many issues including symptoms that may or may not become chronic, many instructions as to what to do next (e.g., follow-up appointments, referrals), and uncertainty regarding the involvement of their oncology team in their health moving forward. Survivorship Care Plans were implemented to help solve these problems.

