6. Insomnia Severity Index (ISI): The ISI is a 7-item questionnaire that assesses sleep quality. It assesses difficulties falling asleep, staying asleep, waking up too early, satisfaction with sleep pattern, how noticeable any sleep problem is to others, worry about sleep problems, and interference of sleep problems with daily functioning. It has been deemed reliable and valid in the cancer population.
7. Global Physical Activity Questionnaire (GPAQ): The GPAQ is a 16-item questionnaire designed to estimate an individual's level of physical activity in three domains: work, transportation, and leisure time, as well as time spent in sedentary behavior. It has been deemed valid and reliable to survey and measure changes in physical activity among many diverse populations. It is commonly used in the cancer literature.
8. Chemotherapy-Induced Peripheral Neuropathy (CIPN-20): The CIPN-20 is a 20-item quality of life questionnaire to elicit patients' experience of symptoms and functional limitations related to numbness, tingling, and other symptoms of chemotherapy-induced peripheral neuropathy.
9. Distress Thermometer (DT): The DT is a self-reported rapid screening tool that uses a rating scale ranging from 0 (no distress) to 10 (extreme distress) that was developed to assess psychological distress in people affected by cancer. Additionally, the patient is prompted to identify sources of distress using a Problem List. This is a very common and useful screening question in the clinic.
10. Healthcare Climate Questionnaire (HCCQ, week 12 only): This is a 6-question survey that inquires about the quality and satisfaction of participants' patient-provider communication. We modified it to ask specifically about oncologist-patient communication regarding healthy lifestyle behaviors.
11. Healthcare Utilization (6 and 12 weeks only): Here, we will inquire about any medical appointments (scheduled or unscheduled), hospitalizations, and out-of-pocket healthcare expenses. We will ask if any of the events was cancer-related or not, or if something in the app triggered the participant to seek medical consultation.
12. Acceptability Survey (6 weeks and post-intervention interview only): We will ask 6 questions to gather feedback about how much the participant liked the app, what features they enjoy/don't use, and if they would recommend it to others.

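### Where sleep is measured by the Insomnia Severity Index, the exploratory sleep associations have insomnia on both sides, which builds in a small upward bias

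*Combined protocol and SAP*

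**What the plan says.** The aims are in Justification, Objective, & Research Design, item 1. The first numbered mechanistic (exploratory) aim is "To assess cross-sectional associations between health behaviors (physical activity, diet, sleep) and cumulative symptom burden at baseline". The second is "To explore associations between changes in health behaviors (physical activity, diet, sleep) and cumulative symptom burden from baseline to 6 weeks", and also to 12 weeks. Neither names the sleep instrument.

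The instruments come from the main aims in the same section. Aim 3 lists "sleep (Insomnia Severity Index), as well as objective measurements of physical activity (e.g., daily steps) and sleep (e.g., sleep quality) from the activity tracker". Aim 2 defines cumulative symptom burden "as measured by the sum of severities of the core patient-reported symptoms from the MD Anderson Symptom Inventory, including fatigue, insomnia, pain" and further symptoms. The description of the ISI under Study Procedures (Questionnaires, number 6) says: "It assesses difficulties falling asleep, staying asleep, waking up too early, satisfaction with sleep pattern".

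Sample Size and Data Analysis, item 2, defines the total as the sum of 13 MDASI symptoms, ranging from 0 to 130. For the exploratory aims it describes only between-arm ANCOVA and mixed models. It gives no method for the behaviour–symptom associations. Nowhere do the documents remove the insomnia item, define a total without it, or mention the overlap.

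**The concern.** The two mechanistic aims ask whether health behaviours go together with symptom burden. If sleep is scored by an insomnia questionnaire and burden by a sum that includes insomnia, some correlation is expected even when sleep is unrelated to every other symptom. The same holds for change: a participant whose insomnia improves lowers both scores at once.

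Two readings are at stake. One is the sleep result itself, which will look somewhat larger than the link between sleep and the other symptoms. The other is any comparison across behaviours, because physical activity and diet share no item with the total and so get no such lift. The study presents these relationships to participants as a reason for the research (Recruitment; Behavioral Intervention, usual care arm).

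**Working it through.** The plan states no expected correlation, power or threshold for these associations, so there is no figure of its own to reproduce.

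**Inputs from the documents**
- 13 items, each on a 0–10 scale, total 0–130; 54 participants planned and 46 evaluable after 15% missing data; two-sided level 0.15, stated under Aim 2 (Sample Size and Data Analysis, item 2).
- SD of the total 17.04, from a similar inventory (same section, item 1).

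**Assumptions, not in the documents**
- The ISI correlates v = 0.8 with the MDASI insomnia item and zero with the other 12 items.
- Items have equal SDs and a common inter-item correlation ρ.

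**Step 1: induced correlation.** In item-SD units the covariance of the ISI with the sum is v, and the variance of the sum is 13 + 13 × 12 × ρ = 13 + 156ρ. So r = v / √(13 + 156ρ).
- ρ = 0: 0.8 / √13 = 0.22
- ρ = 0.2: 0.8 / √44.2 = 0.12
- ρ = 0.3: 0.8 / √59.8 = 0.10

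**Step 2: which ρ fits the plan's SD.** The item SD implied by a total SD of 17.04 is 17.04 / √(13 + 156ρ).
- ρ = 0: 17.04 / 3.606 = 4.73
- ρ = 0.2: 17.04 / 6.648 = 2.56
- ρ = 0.3: 17.04 / 7.733 = 2.20

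An item scored 0–10 cannot have an SD above 5, so ρ = 0 would need nearly every answer to be 0 or 10. The values at 0.2 and 0.3 are plausible, and they are the ones to use.

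**Step 3: chance of a nominal finding.** At n = 54 and two-sided 0.15 the critical |r| is 0.199. Simulated rejection rates:

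| ρ | induced r | 13-item sum | 12-item sum |
|---|---|---|---|
| 0.2 | 0.12 | 30% | 15% |
| 0.3 | 0.10 | 26% | 15% |

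The induced r lies well below the critical value in both rows, so the overlap raises the rate of nominal findings without usually producing one on its own.

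**Step 4: sensitivity.**
- With 46 evaluable participants, as would apply to the change analyses, the rates are about 27% and 25%. This takes the same v and ρ to hold for change scores.
- With v = 0.5 at n = 54 they are about 21% and 19%.
- A different model, in which the insomnia item is itself uncorrelated with the other 12 and v = 0.7, gives r = 0.7 / √(13 + 132c), where c is the correlation among those 12. That is 0.11 at c = 0.2 and 0.10 at c = 0.3, with simulated rates of 27% and 25%.
- Aim 2 lists nine symptoms, while the analysis section counts 13 without itemising them. A nine-item sum would give r = 0.8 / √(9 + 72ρ), which is 0.17 at ρ = 0.2 and 0.14 at ρ = 0.3, so the artefact would be larger.

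**The case against.** The strongest reply has four parts.

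1. *The aims are exploratory and descriptive.* They do not touch Aims 1 to 3 or the effect size carried to the next trial. No test or threshold is set for them, so counting results below p = 0.15 borrows a level given for Aim 2. This stands. It limits the severity, and it makes the 26–30% conditional. The upward bias in the estimate does not depend on any threshold.

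2. *The bias is small.* An r of 0.10 to 0.12 is about 1% of variance (0.10² = 0.010; 0.12² = 0.014). This also stands. A reader might infer that any positive sleep result is uninterpretable, but the figures do not support that: a moderate or strong correlation could not come from this overlap alone. A reader might also take the uncorrelated-items case (r = 0.22, about a 58% chance of a nominal finding) as realistic. Step 2 shows that it does not fit the plan's own SD.

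3. *Sleep is also measured by the activity tracker.* The aims do not name the ISI, and Table 1 ties the tracker to Aim 3 and the ISI to the exploratory aims. This stands, and it confines the point to ISI-based analyses. Tracker sleep shares no questionnaire item with the MDASI and is affected only as far as it follows the self-reported item.

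4. *Insomnia belongs in cumulative burden.* A 12-item total answers a slightly different question. That is true, and it is why the 13-item result should still be shown.

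A reader might extend the point to diet, since appetite loss and nausea are in the total. The documents do not support that. The dietary recall shares no item with the MDASI, and a symptom that alters intake is a real symptom–behaviour relation, which these aims set out to explore.

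**Conclusion.** The concern holds for the ISI-based associations, at baseline and as change to weeks 6 and 12. The overlap follows from the plan's own definitions, and nothing in the documents corrects it. If the ISI correlates 0.8 with the insomnia item and zero with the others, and items intercorrelate at 0.2 to 0.3, the built-in correlation is about 0.10 to 0.12. With n = 54, and if the Aim 2 level of 0.15 is applied, the chance of a nominal finding is about 26% to 30% instead of 15%. That insomnia is a component rests on the Aim 2 symptom list.

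Severity is minor: the aims are exploratory and the bias is modest. It is worth correcting because its direction is known and the remedy costs almost nothing.

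**What to change.** Add one sentence to Sample Size and Data Analysis, item 2: for associations between the ISI and cumulative symptom burden (baseline, change to week 6, change to week 12), the burden score is the MDASI sum without its insomnia item (12 items, 0–120), with the 13-item result reported alongside. Name the sleep instrument used in each analysis.

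Keep the 13-item sum for the associations with tracker-measured sleep, physical activity and diet, and for the Aim 2 outcome.

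The cost is one derived score and one sentence, with no new data. The small downside is that the 12-item total describes burden from symptoms other than sleep, and the report should say so. Writing this down before analysis also avoids a later choice between the two totals.

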Name	Created	Modified Date
-------------	----------------	----------------------

There are no items to display

ID: VIEW4E02805A7E400

Name: v2_Supporting Literature

Study Procedures

If you uploaded a separate research protocol document in the 'Research Protocol' page, cite the applicable section and page numbers from that document in the answer boxes below. (If this study is a collaborative UM/VA study please list each procedure that is being conducted and the locations where it is being conducted.)

- 1 * Describe all procedures being performed for research purposes only (these procedures would not be done if individuals were not in the study) and when they are performed, including procedures being performed to monitor subjects for safety or to minimize risks:

This is a Phase I/II feasibility/preliminary efficacy randomized controlled trial in 54 people with cancer who recently completed chemotherapy or radiotherapy to compare 12 weeks of the POSTHOC app as part of the Survivorship Care Plan (intervention arm, N=36) vs. the usual care Survivorship Care Plan (control arm, N=18). The app does two things: 1) stores information from the Survivorship Care Plan, including diagnosis, treatments, and future plans, and 2) collects data regarding ongoing health status, as it pertains to the Survivorship Care Plan (e.g., nutrition, physical activity, sleep habits, symptoms). Data is collected through a combination of manual entry and automatic collections through a Fitbit wearable device. Future initiatives will allow the app to interface with the electronic medical record to facilitate conversations about lifestyle behaviors between the patient and the clinical care team.

Participants will be randomized 2:1 (intervention: control) to allow us to obtain sufficient data on feasibility and acceptability of the app (with more patients receiving the POSTHOC app), while also obtaining preliminary estimates of the effects of the POSTHOC app vs. usual care on study outcomes by randomizing one third of the patients to control. This will be an open-label study because, due to the nature of the intervention, it is not possible to blind participants. Due to the active involvement of the PI in data acquisition, it is not feasible to blind the PI.

The study activities are briefly described here; the study schema is illustrated in Figure 1 (see Other Attachments, schema.pdf). We will recruit 54 people who have had a diagnosis of cancer through clinics of Co-I [name] and colleagues and other UMMS sites. Recruitment will be feasible over two years. We will recruit from University of Maryland Medical System (UMMS), which includes UMB's Greenebaum Comprehensive Cancer Center, the Cancer Institute at St. Joseph Medical Center, the Tate Cancer Center at Baltimore Washington Medical Center, and other satellite centers. In 2020, 4292 patients received surgery, radiation, and/or chemotherapy through UMMS and would be eligible to receive a Survivorship Care Plan. Even if only 50% had treatment with curative intent, which is a low estimate, and 10% are not eligible for other reasons, 143 patients would be eligible for our study per month. We will not approach all participants who are eligible. Behavioral interventions typically consent 20% of approached patients, and we expect to approach about 25 patients per month to achieve our goal of 3-5 per month for 12-18 months. We will not be able to approach all participants who are eligible because I expect that we will not have adequate resources to screen all providers' schedules each and every week. We will select who to approach based on our available time and resources. We will also select potential participants to approach in order to achieve a diverse participant cohort in regard to cancer diagnoses. Given the large catchment area (over 5 million people) of UMMS and the remote nature of the intervention, we will also be able to recruit patients from sites outside Baltimore, Maryland (e.g., Hagerstown, Waldorf), including patients who live in rural areas.

During the initial meeting with the patient, we will have a member of the study staff explain the purpose of the study and then, if the person is interested in joining the study, obtain their consent for participation. The initial meeting will occur in person, via telephone, or video conference, depending on participant preference. After consent all participants will receive a paper-based Survivorship Care Plan via MyPortfolio. We will administer questionnaires including an On Study form that includes demographics and clinical characteristics and baseline assessments (approximately 35-50 minutes). Questionnaires will be administered via REDCap unless the participant would prefer paper-based questionnaires through the mail. Questionnaires can be completed on any device that has internet, including their computer, tablet, or smartphone, and do not need to be completed in a single sitting; they can be completed on the participants' own time. Participants will receive a Fitbit smartwatch activity tracker and orientation to use of the tracker. Participants will wear the activity tracker for 7 days to assess physical activity and sleep. We will also conduct ecological momentary assessment (EMA) via the activity tracker and POSTHOC app for these 7 days during which participants will be prompted (via notification) to answer 5 questions per day—the default times will be 9am, 12:30pm, 4pm, and 7:30pm but can be adjusted based on the participant's schedule and preferences (ideally begin 1-2 hours after waking). These questions will capture key symptoms—distress, fatigue, pain, numbness/tingling, and interference of any symptoms with daily activity on a scale from 0-10. Dietary intake data will be collected via telephone or video conference by a study team member using the 24-hour (ASA24) Dietary Assessment Tool at baseline, week 6, and week 12.

During the baseline week, all participants will have a "light" version of the POSTHOC app that only has these initial data collection features (e.g., activity tracking, EMA data collection) during the baseline week.

After baseline data collection, participants will be randomized. Randomization will occur 2:1 for POSTHOC app (N=36) vs. control (N=18). We will use a computer-generated table with random blocks of 3 and 6. We will stratify by whether the participant had chemotherapy or not (yes/no).

Both groups: A member of the study team will call each participant approximately once every two weeks for the 12 weeks to encourage engagement, monitor adverse events, and, as appropriate, get feedback on the usability of the app (see Data Collection Table). At 6 and 12 weeks, we will repeat the baseline assessments, including the 35-50 min of questionnaires, wearing the activity tracker for 7 days, EMA for 7 days, and 24-hour dietary assessment.

Intervention (POSTHOC) group: For participants randomized to the POSTHOC group, the intervention consists of the POSTHOC app, which stores an electronic version of the participant's Survivorship Care Plan and has other useful features available to the participant. Specifically, it will list the names and roles of providers, including an oncologist, primary care providers, and any specialists. It will list upcoming appointments and recommendations for future appointments with the target time frames (e.g., annual mammogram for breast cancer, annual CT scan for colorectal cancer). The Survivorship Care Plan always includes healthy lifestyle behavior goals for nutrition (e.g., losing weight or maintaining a healthy weight), exercise (150 minutes per week or 75 minutes of moderate-vigorous physical activity per week), sleep hygiene, and quitting tobacco products. Upon randomization, the coordinator will ensure that the Survivorship Care Plan is properly entered into the app. The participant will choose whether they want to prioritize nutrition or exercise as part of the study. The coordinator will ensure that the participant understands how to read and interpret either the exercise data or food log data in the app in relation to the goals outlined in their Survivorship Care Plan. The participants in the POSTHOC group who choose to focus on exercise will be encouraged to use their activity tracker for the duration of the 12-week intervention period. The POSTHOC app will pull data from the Fitbit app once both apps are installed and set up, so the participant will not need to enter any activity data manually. Survivorship Care Plans tend to recommend 150 minutes per week or 75 minutes of moderate-vigorous physical activity per week or physical activity. We will not provide the exercise group with any materials or specific exercise regimens. We will listen to what their current activity habits are and how they think they would enjoy increasing their activity to reach the goal. Walking 25 minutes per day will achieve the 150 minutes per week goal, and that will be our first recommendation (e.g., outside, at the mall/Walmart/Home Depot, etc.). Participants who choose to focus on nutrition will be encouraged to answer six brief questions at the end of each day regarding their intake of fruits, vegetables, whole grains, and sweets to daily compare their eating habits to their goals. They will meet a member of the study team to brainstorm how to change their current diet to reach the goals. Participants in the POSTHOC+nutrition group will be told that they do not need to wear the activity tracker except for weeks 6 and 12.

Control (usual care) group: The study coordinator will go through the paper-based Survivorship Care Plan with the participant. The control group will keep the "light" version of the POSTHOC app that has minimal data collection features (e.g., activity tracking, EMA data collection). They will be told that they do not need to wear the activity tracker except for weeks 6 and 12.

After completion of the study, participants will be asked to participate in a semi-structured interview during which we will solicit feedback on the study – what they liked about it, what they did not like about it, whether they would recommend it to friends, etc. This will last approximately 30 minutes. Participants will be compensated for their time if they complete at least ¾ of the baseline (\$10), week 6 (\$10), and week 12 (\$30) study activities (7 days of wearing the activity tracker, questionnaires, and responding to prompts on the app) for a total of \$50; we will emphasize the importance of the questions related to symptom burden to answer our primary research questions. As additional compensation, participants will also keep the Fitbit tracker they received upon enrollment in the study. After completion of the study, all participants will be provided with their study data (e.g., EMA assessments, 24-hour dietary assessments) upon request. Those in the usual care group will be provided any study materials related to exercise or nutrition interventions that were provided to the POSTHOC group during the study.

POSTHOC application ("app"). The POSTHOC app is designed to run on both Android and iOS devices that account for more than 90% of all smartphones. A dedicated team of developers will make periodic updates to the app and to the backend server to comply with updates released by Apple and Android.

Clarification as to where activities take place and who is there:

-All activities are planned to be done remotely by default, either via phone or video conference. However, the participant can come to the clinic if they prefer.

-Any discussions (initial meeting, bi-weekly check-ins, post-intervention interview) will be between the study team and the participant at a pre-scheduled time. The questionnaires, wearing the Fitbit, EMA, and daily comparisons of the participants' goals and their actual behaviors will be done by the participant on their own time.

Questionnaires:

Questionnaires will be administered at baseline (Week 0), Week 6, and Week 12. Questionnaires will be administered via REDCap (default) or on paper, and then manually entered into REDCap. There are a total of 14 questionnaires; 12 are self-administered and the remaining 2 are researcher-administered. The On Study form will be completed at baseline only. Healthcare Utilization and Acceptability/Usability of the app will be administered during a routine check-in call at Weeks 6 and 12 only. Acceptability/Usability will be administered to the Intervention group only. The Healthcare Climate Questionnaire (HCCQ) will be administered at week 12 only. The 11 others will be completed at Week 0, Week 6, and Week 12. The battery of questionnaires will include the following:

1. On Study: Demographics and clinical characteristics.
2. MD Anderson Symptom Inventory (MDASI): The 13-item MDASI is a multi-symptom, patient-reported outcome (PRO) symptom assessment scale that assesses the severity of symptoms experienced by patients with cancer and the interference with daily living (e.g., walking, activity, working, housework, relations with other people, enjoyment of life, mood) caused by these symptoms. The sum of the 13-items will be used as the primary aim herein.
3. Functional Assessment of Chronic Illness Therapy-Fatigue (FACT-F): The FACT-F is a 40-item, validated, commonly used measure of fatigue that is comprised of five subscales: physical well-being, social well-being, emotional well-being, functional well-being, and fatigue. It captures symptoms in these categories over the last 7 days.
4. Brief Fatigue Inventory (BFI): The BFI is a 10-item, validated, commonly used measure that captures fatigue now and the usual and worst in the last 24 hours. It also includes 6 single-item questions regarding how fatigue has interfered with general activity, mood, work, etc.
5. Pain Questionnaire: The BPI assesses severity of pain and its impact on functioning. If a person reports feeling pain, it asks what area(s) hurt the most; a pain rating from 0-10 for pain at its least, worse, and average in the last 24 hours; pain right now; medications taken for pain; and how the pain has interfered with general activity, mood, walking, work, relations with other people, sleep, and enjoyment of life. The BPI has been validated in the cancer population and has Cronbach reliability scores that range from 0.77 to 0.91.
6. Insomnia Severity Index (ISI): The ISI is a 7-item questionnaire that assesses sleep quality. It assesses difficulties falling asleep, staying asleep, waking up too early, satisfaction with sleep pattern, how noticeable any sleep problem is to others, worry about sleep problems, and interference of sleep problems with daily functioning. It has been deemed reliable and valid in the cancer population.
7. Global Physical Activity Questionnaire (GPAQ): The GPAQ is a 16-item questionnaire designed to estimate an individual's level of physical activity in three domains: work, transportation, and leisure time, as well as time spent in sedentary behavior. It has been deemed valid and reliable to survey and measure changes in physical activity among many diverse populations. It is commonly used in the cancer literature.
8. Chemotherapy-Induced Peripheral Neuropathy (CIPN-20): The CIPN-20 is a 20-item quality of life questionnaire to elicit patients' experience of symptoms and functional limitations related to numbness, tingling, and other symptoms of chemotherapy-induced peripheral neuropathy.
9. Distress Thermometer (DT): The DT is a self-reported rapid screening tool that uses a rating scale ranging from 0 (no distress) to 10 (extreme distress) that was developed to assess psychological distress in people affected by cancer. Additionally, the patient is prompted to identify sources of distress using a Problem List. This is a very common and useful screening question in the clinic.
10. Healthcare Climate Questionnaire (HCCQ, week 12 only): This is a 6-question survey that inquires about the quality and satisfaction of participants' patient-provider communication. We modified it to ask specifically about oncologist-patient communication regarding healthy lifestyle behaviors.
11. Healthcare Utilization (6 and 12 weeks only): Here, we will inquire about any medical appointments (scheduled or unscheduled), hospitalizations, and out-of-pocket healthcare expenses. We will ask if any of the events was cancer-related or not, or if something in the app triggered the participant to seek medical consultation.
12. Acceptability Survey (6 weeks and post-intervention interview only): We will ask 6 questions to gather feedback about how much the participant liked the app, what features they enjoy/don't use, and if they would recommend it to others.
13. System Usability Scale (SUS) (6 weeks and post-intervention interview only): The System Usability Scale (SUS) is a simple questionnaire giving a global view of subjective assessments of usability. It offers a quick and simple to use questionnaire designed to assess the usability of a particular device or product. The SUS consists of ten usability statements that are rated on a Likert scale of 1 (strongly agree with statement) to 5 (strongly disagree with statement). Answers are coded and a total usability score is derived for the product or device under analysis. The questionnaire also includes an optional free-response comments area.

The self-administered questionnaires that will be completed at Week 0, Week 6, and Week 12 should take approximately 35-50 min in total to complete.

Dietary intake

Dietary intake will be assessed once at baseline, week 6, and week 12. It could occur at the same time as the biweekly check-in or another day that week. The ASA24® Dietary Assessment Tool is a freely available web-based tool used for epidemiologic, interventional, behavioral, or clinical research that enables multiple automatically coded 24-hour dietary recalls. It will be administered by a trained nutritionist via telephone or video conference and takes approximately 30-45 minutes.

Exit interview

After completion of the study (or earlier if a participant withdraws early from the study), a member of the study team will conduct an exit interview to understand the participants' experience of being in the study. We will ask them what they liked about the study, did not like about it, what features they liked/did not like about the POSTHOC app (for those in the intervention arm), if they would recommend the study to others, etc. This interview will be audio-recorded with explicit permission at the time of the interview, then transcribed for qualitative and mixed methods data analysis.

2. * Describe all procedures already being performed for diagnostic or treatment purposes (if not applicable to the study, enter "N/A"):

N/A
3. * Describe the duration of an individual participant's participation in the study:

Participants will participate in the study for approximately 14 weeks, including consent, baseline assessments, a 12-week intervention, and an exit interview.
4. * Describe the amount of time it will take to complete the entire study:

Upon opening of the study, we expect that approximately 3-5 participants will be recruited per month for approximately 14 months. Data originating from questionnaires, activity trackers, the POSTHOC app, and exit interviews will be entered, processed, and cleaned (as applicable) as they come in. Data analysis will take place soon after all data are collected.

These data will be used to inform a follow-on randomized clinical trial, for example, a phase III or multisite clinical trial. These data will also inform design refinements to improve the POSTHOC app toward supporting the needs of target users. It is anticipated that at least two manuscripts will emerge from this study, the first of which will be submitted for publication within one year of the study closing (the primary aims paper).
5. * Describe any additional participant requirements:

None

Sample Size and Data Analysis

If you uploaded a separate research protocol document in the 'Research Protocol' page, cite the applicable section and page numbers from that document in the answer boxes below.

1 * Provide the rationale and sample size calculations for the proposed target population:

This is a two-arm randomized controlled trial that will assess the feasibility of recruitment and retention to a 12-week behavioral health intervention trial facilitated by the POSTHOC app as well as the preliminary efficacy of behavioral health intervention vs. a control arm on the treatment of cumulative symptom burden in people with cancer.

Under assumptions of ANCOVA and pre-post correlation of 0.65 (Born et al., 2007), a sample size of n=46 (after 15% missing data) provides 80% power to detect a standardized between-arm difference of 0.50, which corresponds to a medium-sized and clinically meaningful effect (Norman et al., 2003).

Implications for clinical significance:

The cumulative symptom burden is a sum of the severity of 13 symptoms. It has a range of 0-130. Our power calculation is based on data from a single-arm pilot study that we conducted among a similar group of cancer survivors. In order to achieve a standardized between-arm difference of 0.50, which corresponds to a medium-sized and clinically meaningful effect, we assumed a pre-post correlation of 0.5 (typical for this type of patient-reported outcome). With 80% power, we calculated a minimal sample size of n=46 after an estimated 15% attrition. Effect size (ES) corresponds to how many standard deviations in cumulative symptom burden the groups differ by:

$$ES = (\Delta_{POSTHOC} - \Delta_{control}) / SD_{pooled}$$

$\Delta_{POSTHOC}$ = the difference in cumulative symptom burden from pre- to post-intervention in the POSTHOC group

$\Delta_{control}$ = the difference in cumulative symptom burden from pre- to post-intervention in the control group

SD_{pooled} = the standard deviation of cumulative symptom burden measures for all participants at baseline

From preliminary data generated from a previous study ([name] et al., 2022), we had a standard deviation of cumulative symptom burden from a similar symptom inventory of 17.04.

$$0.50 = (\Delta_{POSTHOC} - \Delta_{control}) / 17.04$$

$$\text{Therefore, } (\Delta_{POSTHOC} - \Delta_{control}) = 8.52$$

Thus, we expect that the cumulative symptom burden will decrease 8.5 points more in the POSTHOC group compared to the control group from baseline to 12 weeks.

2 * Provide the plan for data analysis. Include in the description the types of comparisons that are planned (e.g., comparison of means, comparison of proportions, regressions, analysis of variance, etc.), which is the primary comparison/analysis, and how the analyses proposed will relate to the primary purposes of the study:

Analysis plan for Aim 1. Assess the feasibility of the POSTHOC app by patients newly transitioning from active cancer treatment (n=36). We will calculate the percentage of patients who used the POSTHOC app at least 3 times per week. When we estimate feasibility, a 95% CI will span approximately $\pm 15\%$. For example, if we observe 27/36 (75%) participants used the app, the CI will be 58.9-86.2%.

